12.6 Secondary Efficacy Analyses

12.6.1 *Secondary Efficacy Analysis in the countries of Europe, Australia, New Zealand, and South Africa*

The secondary efficacy analysis will be based on the MITT-M population.

The secondary efficacy analysis is to compare each of the YKP3089 dosage groups with the placebo group for the percent reduction in seizure frequency.

An analysis of covariance (ANCOVA) model will be fit to the ranked values of the change in seizure frequency during the maintenance phase. The ANCOVA will have terms for ranked baseline seizure rate and randomized treatment group. Ties will be handled using the default option in SAS.

It should be noted that the efficacy analysis uses a non-parametric approach. Because of this, effect sizes are not estimated and tested directly, since testing is made on the rank of the change

in seizure frequency. However, summary tables for the actual (not the ranked) change in seizure frequency will be presented.

12.6.2 *Secondary Efficacy Analysis in the United States and the Rest of the World*

The secondary efficacy analysis will be based on the MITT population

The secondary efficacy analysis is to compare each of the YKP3089 dosage groups with the placebo group for the responder rate.

The data will be summarized using frequencies and percents of subjects achieving at least a 50% response to treatment, the responder rate. The responder data will be analyzed using a chi-square test.

12.7 **Additional Secondary Efficacy Analyses**

These secondary efficacy analyses will be based on the MITT or MITT-M population

- Higher response rate of (75, 90 and 100%) of simple partial seizures with motor component plus complex partial seizures plus secondarily generalized tonic clonic seizures during the double-blind period and maintenance phase will be summarized.
- Median percent change for partial seizure subtypes (including simple partial with motor component, complex partial, and secondarily generalized tonic-clonic seizures) will be summarized.
- Seizure rate over time will be analyzed using following scheme
 - A moving average for each dose group will be computed using 4 week periods with 2 week overlap beginning from Visit 3 (V3-V5, V4-V6, V5-V6+2 weeks and so on)
- For the QOLIE-31 analysis, changes from baseline (Visit 3) to the the final value (defined as the last observation obtained in the double-blind phase) (Visit 9) for each treatment group will be summarized using descriptive statistics. Differences between each treatment group and the placebo group in the change from baseline will also be

summarized using descriptive statistics. The minimally important change (MIC) was defined as a change from baseline ≥ 11.8 at the End Point for the weighted overall QOLIE-31 score. The incidence of subjects meeting the MIC criteria will be summarized by treatment group.

- CGIC will be summarized using descriptive statistics for each treatment group and the placebo group.

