	
An analysis of covariance (ANCOVA) model will be fit to the ranked values of the primary efficacy endpoint. The ANCOVA will have terms for ranked baseline seizure rate and randomized treatment group.
 
The primary Efficacy Analysis for Europe, Australia, New Zealand, and South Africa:
 
The primary efficacy analysis of the primary endpoint will be based on the MITT-M population.
 
The testing strategy for the primary efficacy endpoint (responder rate) is to compare each of the YKP3089 dosage groups with the placebo group. A step-down procedure will be used to ensure the type I error rate due to multiple treatment comparisons is controlled at the 5% level. Each of the YKP3089 dosage groups will be compared with the placebo group according to the following hierarchy:
 
1. 200-mg dosage group versus placebo group2. 400-mg dosage group versus placebo group3. 100-mg dosage group versus placebo group 
The 200-mg dosage group will be compared with the placebo group at a 2-sided 0.05 level as the first step. If no statistically significant difference is detected between the 200-mg dosage group and the placebo group, the procedure will stop and it will be concluded that none of the YKP3089 dosages are efficacious. If a statistically significant difference is detected between the 200-mg dosage group and the placebo group in favor of the 200-mg dosage group, the procedure will proceed to the next step to compare the 400-mg dosage group with the placebo group at a 2-sided 0.05 level. If a statistically significant difference is detected between the 400-mg dosage group and the placebo group in favor of the 400-mg dosage group, the procedure will proceed to the next step to compare the 100-mg dosage group with the placebo group at a 2-sided 0.05 level.
 
The data will be summarized using frequencies and percents of subjects achieving at least a 50% response to treatment, the responder rate. The responder data will be analyzed using a chi-square test.
 
Other Efficacy and Safety Analyses:
 
The percentage of subjects who have a 75%, 90% and 100% seizure reduction during the double blind period and the maintenance phase. Responder rates for partial seizure subtypes (including simple partial with motor component, complex partial, and secondarily generalized tonic-clonic seizures) will be summarized. Outcome measurements such as quality of life and clinical global impression change will be analyzed. Safety will be assessed by the frequency, severity, and timing of adverse events, as well as by clinical laboratory test values, 12-lead ECG recordings, vital sign measurements, physical and neurologic

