6.2 Study Endpoints

The primary efficacy endpoints reflect the United States Food and Drug Administration (FDA) recommendation of percent reduction in seizure frequency for registration which is adopted by many countries in the rest of the world, and the European Agency for the Evaluation of Medicinal Products (EMA) recommendation of the responder rate for registration in Europe, which is also adopted by Australia, New Zealand, and South Africa.

6.2.1 *Primary Efficacy Endpoint in the United States and the Rest of the World*

The primary efficacy endpoint to be evaluated for registration in the United States and the Rest of the World is the percent change from the pretreatment baseline phase in seizure frequency (average monthly seizure rate per 28 days) of all simple partial motor, complex partial, or secondarily generalized seizures compared with the double-blind treatment phase.

The baseline rate (B) is calculated by counting the number of seizures over the baseline period and dividing by the number of days in the interval with non-missing seizure data and then multiplying by 28. The double-blind rate (D) is calculated in a similar manner. The percent change is equal to $100 \times (D - B) / B$. Simple partial seizures without a motor/visual component will not be counted.

This value will be undefined if $B = 0$. For the primary efficacy analysis, there will not be any baseline values with zero seizures. However, for the analysis of seizure sub-types, there is a possibility that B may be zero. In this case, B will be set to a value of 1.

6.2.2 *Primary Efficacy Endpoint in the countries of Europe, Australia, New Zealand, and South Africa*

The primary efficacy endpoint to be evaluated for registration in the countries of Europe, Australia, New Zealand, and South Africa is the responder rate defined as a 50% or greater reduction during the maintenance phase of the double blind period in the seizure frequency from baseline.

The responder endpoint is a binary indicator endpoint defined as 1 if the primary endpoint is $\leq -50\%$, and 0 otherwise

6.2.3 *Secondary Efficacy Endpoint in the countries of Europe, Australia, New Zealand, and South Africa*

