The secondary efficacy endpoint to be evaluated for registration in the countries of Europe, Australia, New Zealand and South Africa is the percent change from the pretreatment baseline phase in seizure frequency (average monthly seizure rate per 28 days) of all simple partial motor, complex partial, or secondarily generalized seizures compared with the maintenance phase of the double-blind treatment phase.

The baseline rate (B) is calculated by counting the number of seizures over the baseline period and dividing by the number of days in the interval with non-missing seizure data and then multiplying by 28. The double-blind rate (D) is calculated in a similar manner. The percent change is equal to $100 \times (D-B)/B$. Simple partial seizures without a motor/visual component will not be counted.

This value will be undefined if $B=0$. For the primary efficacy analysis, there will not be any baseline values with zero seizures. However, for the analysis of seizure sub-types, there is a possibility that B may be zero. In this case, B will be set to a value of 1.

6.2.4 *Secondary Efficacy Endpoint in the United States and the Rest of the World*

The secondary efficacy endpoint to be evaluated for registration in the United States and the Rest of the World is the responder rate defined as a 50% or greater reduction during the double blind period in the seizure frequency from baseline. The responder endpoint is a binary indicator endpoint defined as 1 if the primary endpoint is $\leq -50\%$, and 0 otherwise

6.2.5 *Additional Secondary Efficacy Endpoints*

- Higher response rates of (defined by cutoffs of -75%, -90% and -100%) simple partial seizures with motor component plus complex partial seizures plus secondarily generalized tonic clonic seizures during the double-blind period and maintenance phase.

- Percentage change in other seizure types will be calculated in the same way as the primary endpoint except for selecting the specific seizure types:

- o Complex partial
- o Secondarily generalized tonic-clonic
- o Simple partial motor

6.2.6 ***Outcome Measurements***

6.2.6.1 *Clinical Global Impression of Change (CGIC)*

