7.3 Inclusion Criteria

Subjects must satisfy all of the following criteria to be enrolled in the study:

1. Male or female, age 18 to 70 years inclusive
2. Weight at least 40 kg
3. Written informed consent signed by the subject or legal guardian prior to entering the study in accordance with the ICH GCP guidelines. If the written informed consent is provided by the legal guardian because the subject is unable to do so, a written or verbal assent from the subject must also be obtained.
4. A diagnosis of partial epilepsy according to the International League Against Epilepsy's Classification of Epileptic Seizures. Diagnosis should have been established by clinical history and an electroencephalogram (EEG) that is consistent with localization related epilepsy; normal interictal EEGs will be allowed provided that the subject meets the other diagnosis criterion (ie, clinical history).

5. Have uncontrolled partial seizures despite having been treated with at least one AED within approximately the last 2 years.
6. During the 8-week baseline period, subjects must have at least 8 partial seizures including only simple partial seizures with motor component, complex partial seizures, or secondarily generalized seizures without a seizure-free interval of greater than 25 days any time during the 8 weeks baseline. Subjects must have at least 3 of these partial seizures during each of the two consecutive 4-week segments of the baseline period.
7. Currently on stable antiepileptic treatment regimen:
 - a) Subject must have been receiving stable doses of 1 to 3 AEDs for at least 4 weeks prior to screening (Visit 1) to be continued unchanged throughout the study
 - b) Vagal nerve stimulator (VNS) will not be counted as an AED; however, the parameters must remain stable for at least 4 weeks prior to baseline. The VNS must have been implanted at least 5 months prior to Visit 1.
 - c) Benzodiazepines taken at least once per week during the 1 month prior to Visit 1 for epilepsy, or for anxiety or sleep disorder, will be counted as 1 AED and must be continued unchanged throughout the study. Therefore only a maximum of 2 additional approved AEDs will be allowed. See Exclusion Criterion No. 12 for intermittent benzodiazepine rescue parameters.

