12.2 Statistical Methods

Summary statistics and analyses will be presented by the treatment group category assigned to the subject regardless of the dosage of drug administered. Categorical variables will be summarized as frequencies and percentages. Descriptive statistics for continuous variables will include sample size, mean, median, standard deviation, and minimum and maximum values. SAS[®] version 9.2 or later will be used for all data summaries, statistical analyses, and data

listings. Inferential statistical tests will be 2-sided and will employ a tolerance for type I error (alpha, α) of 0.05. Data will be used as collected. Full details of the analysis plan will be included in the Statistical Analysis Plan (SAP) and finalized prior to any un-blinding of efficacy data.

Analyses of Missing Data

The primary efficacy endpoint definition in the United States and Rest of the world states that seizure rates will be calculated using days with non-missing seizure data. The definition does not explicitly account for days with missing data, i.e., days during which the presence or absence of seizures was not recorded in personal diaries. However the definition implicitly accounts for missing data in that it is identical to a definition in which days with missing data are assumed to have the same seizure rate as days with non-missing data.

Similar to the United States definition of the primary efficacy endpoint, the primary endpoint (responder) definition in the countries of Europe, Australia, New Zealand and South Africa implicitly accounts for missing data during maintenance phase in that it is identical to a definition in which days with missing data are assumed to have the same seizure rate as days with non-missing data. An additional analysis will be performed in which subjects who dropped out during the titration phase will be included in the analysis by having their maintenance phase data imputed using the available titration data.

The same approach will be used for missing data in the analysis of all secondary efficacy endpoints.

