12.3 Analysis Data Sets

For all populations, subjects will be analyzed according to the target (randomized) dosage group including subjects who fail to achieve the target dosage during the titration phase.

Enrolled subjects: All subjects who have given informed consent to participate in this study will be considered enrolled subjects.

Intention-to-treat (ITT): All randomized subjects will be considered intention-to-treat subjects.

Modified intention-to-treat (MITT) subjects: All randomized subjects who have taken at least one dose of YKP3089 (or placebo) and have any post-baseline seizure data will be considered modified intention-to-treat subjects.

Modified intention-to-treat (MITT-M) subjects in Maintenance phase: All randomized subjects who have completed the titration phase and have taken at least one dose of YKP3089 (or placebo) in the maintenance phase and have any maintenance phase seizure data will be considered modified intention-to-treat subjects in the maintenance phase.

Per protocol population (PP): All randomized subjects who have no major protocol violations and have at least 80% drug compliance will be considered per-protocol subjects.

Safety evaluable subjects (SE): All ITT subjects.

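### As the protocol is written, a subject who withdraws early with no counted seizure is scored as a 100% responder for the whole double-blind period

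*Protocol*

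**What the plan says.** Protocol 6.2.5 lists among the additional secondary endpoints "Higher response rates of (defined by cutoffs of -75%, -90% and -100%) simple partial seizures with motor component" and the other counted types, over both the double-blind period and the maintenance phase. The Synopsis has the same item: "The percentage of subjects who have a 75%, 90% and 100% seizure reduction during the double blind period and the maintenance phase". Section 12.7 says that the "Higher response rate of (75, 90 and 100%) of simple partial seizures with motor component plus complex partial seizures" and secondarily generalized seizures combined will be summarized in MITT or MITT-M, and names no test.

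The underlying rate is defined in 6.2.1. The baseline rate is the seizure count, "dividing by the number of days in the interval with non-missing seizure data and then multiplying by 28". For treatment, "The double-blind rate (D) is calculated in a similar manner". No minimum number of diary days is set.

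Section 12.2 explains that this is equivalent to giving unrecorded days the same rate as recorded days, and adds: "The same approach will be used for missing data in the analysis of all secondary efficacy endpoints".

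Under 12.3, MITT needs one dose and that the subject "have any post-baseline seizure data". MITT-M needs completed titration, a maintenance dose and some maintenance diary data. Neither set requires completion of the period, and the protocol has no rule that scores withdrawal as non-response.

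**The concern.** Giving unrecorded days the observed rate is a noisy but roughly centred assumption when the endpoint is a rate. It does not carry over to a 100% reduction, which says that no counted seizure occurred in the whole period. One recorded seizure settles that question whenever it occurs. A short empty diary does not settle it, yet the rule scores it as settled in the subject's favour.

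Short empty diaries are plausible here. Inclusion criterion 6 admits uncontrolled subjects "without a seizure-free interval of greater than 25 days any time during the 8 weeks baseline", so gaps of up to 25 days are compatible with eligibility. Protocol 6.1.2.1 allows no dose reduction in Week 1 and directs subjects with significant tolerability problems to discontinue study drug, so some stops can come very early.

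At stake is the meaning of the 100% rate. Readers will take it as freedom from counted seizures over 18 or 12 weeks. If the true figure is near zero, one or two misclassified subjects could be most of what is reported.

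**Working it through.** **The plan's own figure.** The protocol gives no figure for these rates. Its power statement (12.1: 100 per group, 16-point difference, SD 40%, two-sided 0.05) reproduces: 16/(40 × √(2/100)) = 2.83, and Φ(2.83 − 1.96) = 80.7%, against the stated 80%. It does not bear on this point.

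**Score from an empty diary.** Percent change is 100 × (D − B)/B. The entry minimum is 8 seizures in 56 days, so B = 8/56 × 28 = 4. With no seizures, D = 28 × 0/days = 0 and the change is 100 × (0 − 4)/4 = −100%, whether the diary covers 7, 14, 25 or 126 days.

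**Who is affected.** For the 18-week rate it is any MITT subject who withdraws before a first counted seizure. For the 12-week rate it is only subjects who enter maintenance and stop early in it, because titration drop-outs are outside MITT-M. Section 12.2 also plans an additional analysis filling maintenance data from titration data. Whether that extends to these rates is unclear, so it is not counted here.

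**Direction.** At 100%, truncation can add a false responder and cannot remove a true one. At 75% and 90% it can err either way. With B = 4, one seizure in 7 days gives D = 4 and 0% change, so a true 75% responder could be scored a failure. One seizure meets a cut-off c once the diary reaches 28/(B × (1 − c)) days. For 75% this is 28 days at B = 4 and 11.2 days at B = 10. For 90% it is 70 and 28 days.

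**Chance of an empty diary at an unchanged rate.** Poisson counts are assumed: P = exp(−rate × days/28).

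| Days | 4 per 28 days (entry minimum) | 10 per 28 days (assumed) |
|---|---|---|
| 7 | exp(−1) = 37% | exp(−2.5) = 8% |
| 14 | exp(−2) = 14% | exp(−5) = 0.7% |
| 21 | exp(−3) = 5% | exp(−7.5) = 0.06% |
| 84 | exp(−12) = 6 × 10⁻⁶ | negligible |
| 126 | exp(−18) = 1.5 × 10⁻⁸ | negligible |

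**Very early stops.** The protocol gives no withdrawal rate for this trial. The nearest figure is the Phase 2a adverse-event dropout, 4% in each arm (4.4.4). If stops are spread evenly over the first 14 days, the average of exp(−rate × t/28) for t = 1 to 14 is 0.402 at 4 per 28 days and 0.165 at 10. Per 100 subjects:

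- 4% stopping: 100 × 0.04 × 0.402 = 1.6 false responders at 4 per 28 days; 100 × 0.04 × 0.165 = 0.7 at 10.
- 10% stopping: 4.0 and 1.7.

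**Stops over the whole titration phase.** A simulation of 400,000 subjects per cell assumed:

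- Poisson counts.
- Lognormal baseline truncated at 4 per 28 days, median 9.7.
- Lognormal rate ratio with log SD 0.8.
- Median reduction 21% on placebo (Phase 2a) and 37% on active (21 plus the planned 16 points).
- Withdrawal uniform over Days 2-42.

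The true 18-week 100% rate was 0.1-0.2% in each arm. The reported active rate was 0.75% with 5% withdrawing and 1.4% with 10%. The excess is 0.55-0.65 and 1.2-1.3 subjects per 100. A separate run with a baseline median of 11.1 gave 0.8% and 1.4%. If the same withdrawals fall in Days 2-14, the reported rates are 1.5% and 2.8%.

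**The case against.** The strongest reply is that the full analysis rules may lie elsewhere. Protocol 12.2 defers details to the SAP. The SAP supplied covers only the open-label extension and, in its Section 6, points to a separate double-blind SAP that is not available here. A completion or minimum-diary rule may exist there. This stands: the point is about the protocol as written, not about what will certainly be reported.

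The second reply is that little depends on these rates. They are summarized only and lie outside both step-down hierarchies. This also stands.

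The third is that the size depends on choices the documents do not fix. The 37% and 14% chances belong to the entry minimum and fall quickly at higher rates. The baseline median is an assumption. The model uses a 37% active reduction although Phase 2a showed 55%, and it allows no seizure-free subgroup; either would raise the true rate and shrink the relative inflation. The direction of the error is unaffected.

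A reader might infer a dose trend, with false 100% responders rising with dose. The documents do not support that. Under Table 3 all active arms take the same doses through Week 2, and the 200 and 400 mg arms separate only in Week 5, when the chance of an empty diary at 4 per 28 days is about exp(−4) = 1.8%. Some subjects were titrated under the faster scheme described in 4.5.1, but no dropout by dose is given.

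Nor do the documents support a large gap between arms. In the simulation with 5% withdrawal in both arms, reported rates are 0.75% and 0.5%, a difference of 0.25 points against a true difference of about 0.1. A gap near 2 points needs 20% withdrawal on active (reported 2.6%) against 5% on placebo, which no section suggests.

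**Conclusion.** The concern holds for the 100% rate. Protocol 6.2.1, 6.2.5, 12.2, 12.3 and 12.7 together state a rule under which an early withdrawal with an empty diary is a 100% responder for 18 weeks in MITT, or for 12 weeks in MITT-M if the stop comes early in maintenance. The error runs one way. Its likely size is about one subject per 100-subject arm, on the assumptions of Poisson counts, the simulated baseline distribution and 5-10% withdrawal over Days 2-42. It is larger if stops cluster in the first two weeks. No size was derived for the 12-week rate.

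Two wider readings should be resisted. Titration drop-outs do not inflate the 12-week rate, because they are not in MITT-M. The 75% and 90% rates do not share the one-way error, so the same remedy there would exchange an error in both directions for a guaranteed downward one. This is worth correcting before reporting, but it does not touch the primary tests or any tested secondary endpoint.

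**What to change.** In Protocol 6.2.5 and 12.7, state that a subject counts as a 100% responder for the double-blind period, or for the maintenance phase, only if the subject completed that period with no counted seizure. Subjects who withdrew before its end stay in the MITT or MITT-M denominator as not achieving 100%. Exempt this rate from the sentence in 12.2 that extends the missing-data approach to all secondary endpoints. If the double-blind SAP already contains a rule, align the two documents. Leave the 75% and 90% rates without a completion condition.

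The cost is one sentence and a completion flag in the program. The downside is that a subject who was truly seizure-free but withdrew for another reason counts as not achieving 100%, so the reported rate will be slightly lower.
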